2.1.4. Clinical Safety of Encorafenib in Combination with Binimetinib

COLUMBUS results demonstrated improved tolerability in the encorafenib 450 mg QD + binimetinib 45 mg BID arm compared with single-agent encorafenib 300 mg QD (Dummer et al, 2018a; Dummer et al, 2018b). This is consistent with a body of literature that suggests the combination of a BRAF inhibitor and a MEK inhibitor results in improved tolerability compared with either agent alone (Flaherty et al, 2012; Long et al, 2014; Robert et al, 2015; Larkin et al, 2014; Ascierto et al, 2016).

Among patients receiving encorafenib plus binimetinib combination therapy in the COLUMBUS study, the most common adverse reactions ($\geq 20\%$ of patients, all grades) were fatigue (43%), nausea (41%), diarrhea (36%), vomiting (30%), abdominal pain (28%), arthralgia (26%), myopathy (23%), hyperkeratosis (23%), rash (22%), headache (22%), constipation (22%), visual impairment (20%) and serous retinopathy (20%). Most of these toxicities were generally reversible and manageable by supportive medical care, dose modifications or discontinuation. Other clinically important adverse reactions occurring in < 10% of patients were facial paresis, pancreatitis, panniculitis, drug hypersensitivity and colitis. The most common laboratory abnormalities ($\geq 2\%$, Grade 3 or 4) were increased GGT (11%), increased ALT (6%), increased creatine phosphokinase (5%), increased fasting glucose (5%), increased creatinine (4%), anemia (4%), hyponatremia (4%), increased AST (3%), neutropenia (3%) and lymphopenia (2%). Detailed information regarding clinical safety is presented in the respective Investigator's Brochures for encorafenib and binimetinib.

Important potential adverse effects associated with the administration of the combination of encorafenib and binimetinib established primarily from safety data from the COLUMBUS study and, where indicated, from other studies of the combination, include:

- New primary malignancies: Based on its mechanism of action, encorafenib may promote malignancies associated with activation of *RAS* through mutation or other mechanisms. Cutaneous and non-cutaneous malignancies occurred in patients, including cutaneous squamous carcinoma/keratoacanthoma (2.6%; median time to first occurrence of 5.8 months) and basal cell carcinoma (1.6%).

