3. OBJECTIVES AND ENDPOINTS

Table 5.Objectives and Endpoints

| Primary Objective | Primary Endpoint | |
|---|--|--|
| • To evaluate the efficacy of encorafenib + binimetinib in treatment-naïve and previously treated patients with BRAF ^{V600E} -mutant NSCLC as measured by ORR | • ORR defined as the proportion of patients who have achieved a confirmed best overall response (CR or PR) as determined by IRR per RECIST v1.1 in the treatment-naïve setting | |
| | • ORR defined as the proportion of patients who have achieved a confirmed best overall response (CR or PR) as determined by IRR per RECIST v1.1 in the previously treated setting. | |
| Secondary Objectives | Secondary Endpoints | |
| • To evaluate the efficacy of encorafenib + binimetinib in treatment-naïve and previously treated patients with BRAF ^{V600E} -mutant NSCLC as measured by DOR, DCR, PFS, and TTR | Confirmed ORR by Investigator per RECIST v1.1 DOR (by IRR and by Investigator) defined as the time from the date of the first documented response (CR or PR) that is subsequently confirmed (by IRR and by Investigator, respectively) to the earliest date of disease progression, per RECIST v1.1, or death due to any cause DCR (by IRR and by Investigator), defined as the proportion of patients who have a confirmed CR or confirmed PR, or SD per RECIST v1.1 PFS (by IRR and by Investigator), defined as the time from the date of first dose of study drug to the earliest date of disease progression, per RECIST v1.1 PTR (by IRR and Investigator), defined as the time from the date of first dose to the first documentation of objective response (CR or PR) which is subsequently confirmed (by IRR and by Investigator), defined as the time from the date of first dose to the first documentation of objective response (CR or PR) which is subsequently confirmed (by IRR and by Investigator) | |
| • To evaluate the efficacy of encorafenib + binimetinib in treatment-naïve and previously treated patients with BRAF ^{V600E} -mutant NSCLC with respect to OS | • OS defined as the time from the date of first dose of study drug to the date of death due to any cause | |
| • To evaluate the safety and tolerability of encorafenib + binimetinib in treatment-naïve and previously treated patients with BRAF ^{V600E} -mutant NSCLC | • Incidence and severity of AEs graded according to the NCI CTCAE v4.03 and changes in clinical laboratory parameters, vital signs, ECGs and ECHO/MUGA scans | |

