8.4.3. Safety Analyses

Safety data will be presented, based on the SS, in tabular and/or graphical format and summarized descriptively, where appropriate. Adverse events will be coded using MedDRA®. The incidence of AEs will be summarized by system organ class and/or preferred term, maximum severity (based on CTCAE grades), type of AE and relation to study treatment.

Laboratory parameters will be presented in shift tables of baseline grade vs. maximum grade on study. For laboratory parameters that are not gradable by CTCAE, shift tables of normalabnormal will be provided. Summaries of clinically notable measurements will also be provided. Definitions of clinically notable will be provided in the SAP.

Vital signs, body weight, ECOG PS, ECHO/MUGA and select ophthalmic examination data will be summarized.Clinically notable vital sign measurements will be summarized. Definitions of clinically notable will be provided in the SAP.

Results for each ECG parameter will be summarized and reviewed for clinically notable abnormalities according to predefined criteria as outlined in the SAP.

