 - Preexisting values of TBili above the normal range: TBili level increased from baseline value by an amount of at least 1 × ULN or if the value reaches >3 × ULN (whichever is smaller).

Rises in AST/ALT and TBili separated by more than a few weeks should be assessed individually based on clinical judgment; any case where uncertainty remains as to whether it represents a potential Hy's law case should be reviewed with the sponsor.

Version 5

The patient should return to the investigator site and be evaluated as soon as possible, preferably within 48 hours from awareness of the abnormal results. This evaluation should include laboratory tests, detailed history, and physical assessment.

In addition to repeating measurements of AST and ALT and TBili for suspected cases of Hy's law, additional laboratory tests should include albumin, CK, direct and indirect bilirubin, GGT, PT/INR, total bile acids, and alkaline phosphatase. Consideration should also be given to drawing a separate tube of clotted blood and an anticoagulated tube of blood for further testing, as needed, for further contemporaneous analyses at the time of the recognized initial abnormalities to determine etiology. A detailed history, including relevant information, such as review of ethanol, acetaminophen/paracetamol (either by itself or as a coformulated product in prescription or over-the-counter medications), recreational drug, supplement (herbal) use and consumption, family history, sexual history, travel history, history of contact with a jaundiced person, surgery, blood transfusion, history of liver or allergic disease, and potential occupational exposure to chemicals, should be collected. Further testing for acute hepatitis A, B, C, D, and E infection and liver imaging (eg, biliary tract) and collection of serum samples for acetaminophen/paracetamol drug and/or protein adduct levels may be warranted.

All cases demonstrated on repeat testing as meeting the laboratory criteria of AST/ALT and TBili elevation defined above should be considered potential DILI (Hy's law) cases if no other reason for the LFT abnormalities has yet been found. Such potential DILI (Hy's law) cases are to be reported as SAEs, irrespective of availability of all the results of the investigations performed to determine etiology of the LFT abnormalities.

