7.6.5. Clinical Laboratory Evaluations

Required hematology, coagulation, urinalysis and clinical chemistry tests are described in Table 11 of the protocol. Hematology, coagulation, urinalysis and clinical chemistry test results will be presented using the International System of Units (SI units) and, where appropriate, will be graded using NCI CTCAE, Version 4.03.

For laboratory data, baseline is the last available assessment performed prior to the treatment start date/time. If more than one value is available, priority is given to the central assessment versus the local assessment. If more than one central sample is available, priority is given to the assessment marked as *Unscheduled* or *Repeat* assessment. Participants who start treatment and discontinue from the study on the same day may have 2 different sets of data collected on study day 1, one being reported to the cycle 1 day 1 visit, the other reported to the EOT visit. Data reported at the EOT visit are not eligible for baseline selection.

The following laboratory parameters will be summarized by CTCAE grade:

- Hematology: Hemoglobin (anemia/hemoglobin increased), Platelets (platelet count decreased), WBC (white blood cell decreased/increased), Neutrophils (neutrophil count decreased), Lymphocytes (lymphocyte count increased/decreased).
- Chemistry: Albumin (hypoalbuminemia), Alkaline phosphatase (ALP) (alkaline phosphatase increased), Alanine aminotransferase (ALT) (ALT increased), Aspartate aminotransferase (AST) (AST increased), Total bilirubin (TBL) (blood bilirubin increased), Creatinine (creatinine increased), Corrected calcium, CK, Amylase (serum amylase increased), Lipase (lipase increased), Phosphate (hypophosphatemia),

Magnesium (hypomagnesemia/hypermagnesemia), Potassium (hypokalemia/hyperkalemia), Sodium (hyponatremia/hypermnatremia).

- Coagulation: INR (INR increased), PTT or aPTT (Activated partial thromboplastin, time prolonged)

The following laboratory parameters will be summarized by normal range:

- Hematology: Hematocrit, RBC, Monocytes (absolute), Eosinophils (absolute), Basophils (absolute).
- Chemistry: Bicarbonate (CO₂), BUN or urea, Chloride, Glucose, LDH, Total protein, Direct bilirubin.
- Coagulation: Prothrombin Time

The Corrected Calcium will be derived from calcium and albumin results as per the following formula:

$$\text{Corrected Calcium (mmol/L)} = [4 * \text{calcium (mmol/L)} - 0.8 * (0.1 * \text{albumin (g/L)} - 4)] / 4$$

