The normal range of Calcium will be used as normal range for Corrected Calcium.

The following summaries will be produced for the hematology and chemistry laboratory data (by laboratory parameter) including central and local laboratory:

- Shift tables using CTCAE grades to compare baseline to the worst post-baseline value for laboratory parameters with CTCAE grades. For the laboratory parameters like blood sodium where participants can be graded for decreased or increased values, the worst post-baseline CTCAE grade will be presented for decrease and increase separately (e.g. hyponatremia and hypernatremia).
- Shift tables using CTCAE grades to compare baseline to the worst post-baseline value for laboratory parameters with CTCAE grades showing participants with Grade ≤ 2 at baseline and worst post baseline Grade 3 or 4.
- Tables reporting the worst post-baseline CTCAE grades for laboratory parameters.
- Shift tables using low, normal, high (as well as low and high combined) classifications to compare baseline to the worst post-baseline value for laboratory parameters where CTCAE grades are not defined.

The following listing will be produced for the laboratory data for all laboratory parameters are defined:

- All laboratory test results will be presented in listings sorted by participant identifier, laboratory test, and date/time of collection with values flagged to show the corresponding CTCAE grades and the classifications relative to the laboratory

reference ranges. Values outside laboratory normal ranges will be flagged where appropriate.

Hepatic Toxicity

Hepatic toxicity will be assessed based on the following Liver Function Tests (LFTs): ALT, AST, ALP, TBL, and INR. Frequency counts and percentages of participants having a newly occurring value in the categories in Table 6 will be provided.

An evaluation of Drug-Induced Serious Hepatotoxicity (eDISH) plot will also be created by graphically displaying

- peak serum ALT(/ULN) vs peak total bilirubin (/ULN) including reference lines at ALT =3×ULN and total bilirubin =2×ULN.
- peak serum AST(/ULN) vs peak total bilirubin (/ULN) including reference lines at AST =3×ULN and total bilirubin =2×ULN.

In addition, a listing of all LFTs values for participants having a newly occurring value in the categories presented in Table 6 will be provided.

Table 6. Hepatic Toxicity Criteria

Parameter	Criterion
ALT	>3xULN; >5xULN; >8xULN;>10xULN;>20 ULN
AST	>3xULN; >5xULN; >8xULN >10xULN;>20 ULN

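### Glucose is tabulated only as low, normal or high, although the plan's own rule calls for CTCAE grades and the protocol cites Grade 3-4 glucose increases in 5%

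*SAP*

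**What the plan says.** Part of the secondary safety endpoint (Protocol section 3) is "Incidence and severity of AEs graded according to the NCI CTCAE v4.03 and changes in clinical laboratory parameters", followed by vital signs and cardiac measures.

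Protocol 8.4.3 sets the rule for laboratory tables: "Laboratory parameters will be presented in shift tables of baseline grade vs. maximum grade on study". Normal-abnormal shift tables are for parameters that CTCAE cannot grade. The same section promises summaries of clinically notable laboratory values.

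SAP 7.6.5 has two lists, one summarised by CTCAE grade and one by normal range. Glucose is in the second, alongside "BUN or urea, Chloride, Glucose, LDH, Total protein, Direct bilirubin". For that list the planned output is "Shift tables using low, normal, high (as well as low and high combined) classifications to compare baseline to the worst post-baseline value", which the SAP says is for parameters that have no CTCAE grades.

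Protocol 2.1.4 gives the commonest Grade 3 or 4 laboratory abnormalities with this combination in the melanoma trial. They "were increased GGT (11%), increased ALT (6%), increased creatine phosphokinase (5%), increased fasting glucose (5" (the quotation stops inside the bracket; the glucose figure is 5%).

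SAP section 6 lists the changes from the protocol. For laboratory data it names only the removal of the clinically notable summaries.

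**The concern.** The plan states a rule twice and then does not follow it for one parameter. The protocol itself quotes a Grade 3-4 frequency for glucose, so the sponsor treats it as gradable. The SAP nevertheless handles it as ungradable, without giving a reason and without declaring the departure.

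The normal-range table has one category above normal. A participant with a severely raised glucose and one marginally above the upper limit of normal fall in the same cell. The summary of clinically notable values could have told them apart, but it has been removed. What is at stake is one safety summary: a reader could not set the laboratory-based Grade 3-4 glucose frequency in this lung cancer population beside the figure quoted in Protocol 2.1.4.

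**Working it through.** The plan gives no figure of its own to reproduce here. The check matches lists, traces outputs and then gives an illustrative size.

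**1. Match the protocol's list to the SAP's lists.** The ten items come from Protocol 2.1.4, the scheduled tests from Protocol Table 11, and the handling from SAP 7.6.5.

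| Abnormality (Grade 3-4 rate) | In Table 11 | SAP 7.6.5 list |
|---|---|---|
| GGT (11%) | no | none |
| ALT (6%) | yes | graded |
| CPK (5%) | yes | graded |
| Fasting glucose (5%) | yes, as glucose | normal range |
| Creatinine (4%) | yes | graded |
| Anemia (4%) | yes | graded |
| Hyponatremia (4%) | yes | graded |
| AST (3%) | yes | graded |
| Neutropenia (3%) | yes | graded |
| Lymphopenia (2%) | yes | graded |

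Scheduled: 10 - 1 = 9. Of those 9, graded: 8. The only one measured on schedule but not graded is glucose (9 - 8 = 1).

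**2. Apply the rule.** Under Protocol 8.4.3, and under SAP 7.6.5's own description of the low/normal/high table, that format is for parameters without grades. Protocol 2.1.4 reports grades for increased fasting glucose. By the documents' own usage, glucose belongs in the graded list unless a reason is stated. None is stated.

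**3. Trace every planned output that could show a severe value.**
- Grade shift table, worst-grade table, and the shift table from Grade 2 or lower to Grade 3 or 4: these use the graded list, so glucose is not in them.
- Low/normal/high shift table: glucose is included, with no severity above normal.
- Clinically notable laboratory summary: removed by SAP section 6.
- By-participant listing: all results are included, with CTCAE grades to be flagged, but a listing gives no rate.
- Graded adverse event tables (SAP 7.6.4): glucose events appear only if the investigator recorded them as adverse events.

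**4. Illustrative size.** Inputs: rate 5% (Protocol 2.1.4; melanoma, fasting glucose), and treated participants from 60 + 37 = 97 to 107 (Protocol 8.2, SAP 4.3).

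Expected number = n x rate:
- 97 x 0.05 = 4.85
- 107 x 0.05 = 5.35

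Chance of at least one case = 1 - (1 - rate)^n:
- 1 - 0.95^97 = 0.993
- 1 - 0.95^107 = 0.996

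If the rate here were only 2%, the threshold for entry to the Protocol 2.1.4 list, the expected number would be 97 x 0.02 = 1.94 to 107 x 0.02 = 2.14. So the expected number is about 2 at 2%, and about 5 at the quoted rate.

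**The case against.** **Fasting status.** This is the best argument for the SAP as written. Protocol 2.1.4 refers to fasting glucose, Table 11 says only glucose, and study drug is taken without regard to food (Protocol 6.1.1 and 6.1.2). No fasting requirement appears for the draws, and SAP 7.6.5 grades only where this is appropriate. The sponsor may have judged that values of unknown fasting status should not be graded. That would be a legitimate reason, but it is not written down. It calls for a stated grading rule and a footnote, not an unexplained loss of grades. It does stand as a limit on the 5% projection.

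**Other routes.** A reader might infer that severe glucose values would be invisible. The documents do not support that. The listings cover every laboratory result, so a grade can be derived. Appendix 4 requires an abnormal laboratory result to be recorded as an adverse event if, for example, it has accompanying symptoms or needs intervention, and Grade 3 and 4 events are tabulated by preferred term. What stands is narrower: neither route gives a laboratory-based rate, and the second depends on investigator reporting.

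**Latitude.** Protocol section 8 lets the SAP modify methods, and the endpoint speaks of changes in laboratory parameters without promising a Grade 3-4 rate for each one. Both are true. Neither explains why section 6, which exists to record such changes, omits this one.

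**GGT.** A reader might infer a second gap of the same kind, because GGT heads the list at 11% and is in neither SAP list. The documents do not support treating it as an analysis error, nor saying that it is never measured. It is outside the scheduled panel, but Appendix 5 requests it when a possible Hy's law case is worked up: "additional laboratory tests should include albumin, CK, direct and indirect bilirubin, GGT". The SAP's hepatic analysis rests on ALT, AST, ALP, total bilirubin and INR. Adding GGT would be a monitoring preference. SAP version 3.0 also follows the first interim analysis, so values from earlier visits could not be recovered. At most it is a limitation to note.

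**Conclusion.** The concern holds for glucose. SAP 7.6.5 departs, undeclared, from a rule that Protocol 8.4.3 and the SAP itself both state. With the clinically notable summaries withdrawn, no planned laboratory table distinguishes a severe glucose value from a trivial one. This follows from the text and does not depend on any assumed rate.

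The size, about 5 of 97 to 107 participants, assumes that the melanoma-trial rate carries over to lung cancer and that a rate for fasting glucose applies to draws of unknown fasting status. It is an order of magnitude, not a forecast.

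The consequence is limited to one safety summary. The primary endpoint and the sample size are untouched. A reader might also infer that the regimen's claimed safety advantage depends on this table, but Protocol 1.1 and 2.2 argue that advantage mainly from pyrexia and photosensitivity.

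**What to change.** In SAP 7.6.5:
- Move glucose from the normal-range list to the CTCAE-graded list, with high and low values shown separately, as the SAP already does for sodium.
- Include it in the worst post-baseline grade table and in the shift table from Grade 2 or lower at baseline to Grade 3 or 4.
- Add a footnote stating how non-fasting values, and values of unknown fasting status, are graded.

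If the sponsor prefers to keep glucose ungraded, SAP section 6 should declare the departure and give the reason.

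The cost is SAP wording and table programming on data already collected; no new samples or assays are needed. The downside is small: lower grades may be misclassified where fasting status is unknown, which the footnote should say.

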7.6.6. Vital Signs and Body Measurements

The following criteria define clinically notable vital sign abnormalities:

Clinically notable elevated values

- Systolic Blood Pressure (BP): ≥ 160 mmHg and an increase ≥ 20 mmHg from baseline
- Diastolic BP: ≥ 100 mmHg and an increase ≥ 15 mmHg from baseline
- Pulse rate: ≥ 120 bpm with increase from baseline of ≥ 15 bpm
- Weight: increase from baseline of $\geq 10\%$
- Body temperature [C]: ≥ 37.5 C

Clinically notable low values

- Systolic BP: ≤ 90 mmHg with decrease from baseline of ≥ 20 mmHg
- Diastolic BP: ≤ 50 mmHg with decrease from baseline of ≥ 15 mmHg
- Pulse rate: ≤ 50 bpm with decrease from baseline of ≥ 15 bpm
- Weight: $\geq 20\%$ decrease from baseline
- Body temperature [C]: ≤ 36 °C

Number and percentage of participants with at least one post-baseline vital sign abnormality will be summarized.

In addition, a table reporting the worst post baseline CTCAE grade for temperature will be produced showing: Grade 0 (≤ 38.0 °C), Grade 1 ($> 38.0 \leq 39.0$ °C), Grade 2 ($> 39.0 \leq 40.0$ °C), Grade 3 or 4 (> 40.0 °C).

7.6.7. ECG

Potential effects of treatment with study drug on ECG parameters will be assessed by ECG interval analysis of heart rate, QRS, QT, and QT interval corrected for heart rate using Fredericia's formula (QTcF). Triplicate measurements will be obtained at screening and pre-dose on Cycle 1 Day 1 according to the schedule of assessments in the protocol.

The average of the machine-read triplicate ECG measurements collected closest to but prior to the first dose of study drug will serve as each participant's baseline QTcF value for all post-dose comparisons. The QTcF data collected on the eCRF page will be used in the summary.

Data from ECGs will be listed, notable values will be flagged, and any other information collected will be listed as appropriate. Frequency counts and percentages of participants having clinically notable ECG values according to [Table 7](#) will be provided.

Table 7. Criteria for Clinically Notable ECG Criteria

Parameter	Criterion
QTcF	increase from baseline > 30 ms
	increase from baseline > 60 ms
	new > 450 ms
	new > 480 ms
	new > 500 ms

